study will not only inform evidence-based guidelines but also address the wide variations in practice patterns that suggest clinical uncertainty in treating non-daily smokers. The proposal has been identified as important by patient and clinician groups. Throughout the course of our ongoing smoking cessation programs at Swope Health Central, one of two recruitment sites for this study, a growing number of AA smokers were being excluded because of their non-daily smoking status, and we received countless requests for help from AA non-daily smokers. At the same time, providers expressed concern about the lack of evidence-based recommendations for treating non-daily smokers and the need for a quit smoking program to meet the demands of this growing patient population. The study is directly derived from these requests. Finally, the experience of our group, our previous success using research finding to change policy/practice, and integration of the CART decision tree (Aim 3) into electronic medical records will ensure that the findings, whether positive or negative, are disseminated quickly and affect changes in current practice. A distinct advantage of this proposal is that its ability to impact practice is not tied to finding group differences in the hypothesized directions (Aims 1, 2). Rather, independent of whether there is an overall difference between groups in treatment efficacy, our decision tree will identify subgroups for whom treatment efficacy differs. Some patients may benefit most from counseling only, others may benefit from counseling and nicotine patch, and others may benefit from counseling and gum or lozenge. Our decision tree will identify these subgroups, allow patients and providers to estimate an individual's chance of success given their treatment and select patient characteristics (e.g., gender, age, menthol versus non-menthol cigarettes, nicotine dependence, nicotine intake, polytobacco versus cigarette only use), and can be directly implemented into clinical practice.

C. Rationale

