C. Sample size, statistical methods, and power calculation

384 AA non-daily smokers will be randomized. We will use 2:1 randomization; for every patient randomized to C, two will be randomized to C+NRT (see Figure). Randomization will be determined by computer-generated random numbers generated by [name]. Randomization assignments will be placed in sealed envelopes by a member of [name] team with sequential study ID numbers. After baseline data collection has been completed, the research assistant will select the sequential study ID number from the sealed envelope to determine the randomization assignment.

The maximum number of participants enrolled in C will be 128 and the maximum number enrolled in C+NRT will be 256. Our sample size is based on our primary outcome, biochemically confirmed point-prevalence abstinence at Week 12 using an intent-to-treat approach. Based on treatment studies with AA light smokers who have received tobacco treatment guideline-based counseling and no pharmacotherapy, we expect a 10% point prevalence abstinence rate in the C group and a 20-25% point prevalence abstinence rate in the C+NRT group based on recent meta-analyses and studies examining the effectiveness of these medications in AA light smokers.^{11,28,45,46} Using the chi-square test, along with the assumptions above, 256 participants in the C+NRT group and 128 participants in the C group (n=384), we will have 95% power to detect an increase from 10% to 25% in cessation at Week 12 between C and C+NRT, 87% power to detect a and increase from 10% to 22.5%, and 71% power to detect an increase from 10% to 20% with a type 1 error rate of 5%.

Analysis Plan for Each Aim

All primary analyses on smoking cessation will be conducted using intent-to-treat and will code those lost to follow-up as smokers. Subsequently we will evaluate the missing data pattern. If there is a differential loss based upon group, multiple imputation techniques will also be used.

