Specific Aim 3: Identify subgroups of AA non-daily smokers for whom the relative benefits of treatment might differ. We will employ a Classification and Regression Tree decision tree modeling on Week 12 verified smoking status (quit versus not quit) to identify subgroups of participants whose personal characteristics might impact the benefit of treatment. The resulting decision tree will allow smokers and their providers to estimate their individual chances of success given their choice of treatment. To maximize the utility of the decision tree, we solicited input from our Stakeholder Advisory Committee and Patient Advisory Panel and included the demographic, smoking, and treatment-related variables identified by them (see Measures and Time Points Table) for possible inclusion in the predictive model. The candidate variables, along with treatment assignment (C, C+NRT) will be entered into a recursive partitioning model as described by Brieman and Freidman using the RPART package in the R statistical software.⁴⁷ Specific methods related to building the tree (using appropriate splitting criteria and loss incorporation using the altered priors method), pruning the tree and handling missing data (using surrogate variables) will be deployed using the techniques described by Therneau et al.⁴⁸ Given the cessation rate expected and overall sample size, a validation subsampling scheme will not be feasible, thus we will utilize 10-fold cross-validation on the regression tree to assess its properties. Additionally, we will account for the uncertainty in tree classification by

generating a bootstrap sampling distribution of the predictive as described by Shalizi.⁴⁹ Modeling cessation was of greatest interest for our initial Patient and Stakeholder Advisory Panels, but other outcomes (reduction in nicotine or carcinogen exposure) could be modeled if our patients and stakeholders think that these additional models might be useful.

D. Subject Criteria (See Vulnerable Populations appendix, if applicable)

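### The Aim 3 tree is promised to find subgroups with differing treatment efficacy and is headed for medical records, yet nothing decides when it may be used, and the unstated loss and pruning rule decide whether chance splits survive

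*Combined protocol and SAP*

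**What the plan says.** Two statements in the Significance part of I.B set out the use of the tree. One is that "integration of the CART decision tree (Aim 3) into electronic medical records will ensure that the findings, whether positive or negative, are disseminated quickly". The other is that "independent of whether there is an overall difference between groups in treatment efficacy, our decision tree will identify subgroups for whom treatment efficacy differs". The same paragraph says the tree will let patients and providers estimate an individual's chance of success and can go straight into practice.

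The method is in II.C, Specific Aim 3. Candidate variables and treatment assignment enter an rpart model of verified Week 12 quit status. The plan names "loss incorporation using the altered priors method" but gives no loss values. It plans pruning, by reference to a cited rpart source, but states no rule. On validation it says that "a validation subsampling scheme will not be feasible, thus we will utilize 10-fold cross-validation on the regression tree to assess its properties". A bootstrap distribution of the prediction is also planned to express uncertainty.

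The available text sets no minimum cross-validated performance, no comparison with the two arm rates, no outcome for a tree without splits, and no condition for entry into medical records.

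**The concern.** A tree grown on few events from many candidates can split on noise. The plan has tools that would reveal this, but it does not say what they must show before the tree is used. I.B meanwhile announces in advance that subgroups will be found.

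Two things are at stake. Patients and providers could be shown individual chances of success that differ only by chance. Separately, a tree that merely predicts who quits could be presented as showing who benefits from NRT, because nothing in the Aim 3 plan tests whether the treatment effect differs between leaves.

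**Working it through.** **Inputs.** From II.C: "The maximum number of participants enrolled in C will be 128 and the maximum number enrolled in C+NRT will be 256", and "we expect a 10% point prevalence abstinence rate in the C group and a 20-25% point prevalence abstinence rate in the C+NRT group". Participants lost to follow-up count as smokers, so all 384 contribute.

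**The plan's own figure first.** It states "95% power to detect an increase from 10% to 25% in cessation at Week 12 between C and C+NRT". A two-sided pooled chi-square at 5% uses:
- Pooled rate = (128×0.10 + 256×0.25)/384 = 0.20.
- Null SE = √[0.20×0.80×(1/128 + 1/256)] = 0.0433.
- Alternative SE = √[0.09/128 + 0.1875/256] = 0.0379.
- Power = Φ[(0.15 − 1.96×0.0433)/0.0379] = 95.7%.

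The same formula gives 87.6% at 22.5% and 71.7% at 20%, against 87% and 71% stated. The inputs reproduce.

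**Events.** The C arm gives 128×0.10 = 12.8 quitters. C+NRT gives 256×0.20 = 51.2 to 256×0.25 = 64.0. The total is 64.0 to 76.8.

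**Candidates.** The covariate list in the Measures table has 6 demographic and 9 smoking-history variables. With treatment that makes about 16; NRT choice and nicotine intake could add one or two. Quitters per candidate: 64.0/16 = 4.0 to 76.8/16 = 4.8. For the Aim 1 covariate model, the plan itself foresees no more than six covariates, citing sample size and expected quitting. Aim 3 has no comparable limit.

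**Why the loss matters.** If missing a quitter costs L times the opposite error, a leaf is labelled quit when its rate exceeds 1/(1+L): 50% at 1:1, 25% at 3:1, 20% at 4:1. Class-balanced loss is (384 − 64)/64 = 5:1 at 64 quitters and (384 − 76.8)/76.8 = 4:1 at 76.8. At 3:1 or less the threshold is at or above the highest expected arm rate (25%), so even the split on arm gains little. That is a natural reason to choose a heavier loss, and a heavier loss brings the threshold into the range where chance variation between leaves changes their label.

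**Simulation.** 384 participants, arm plus 15 independent noise covariates, 10-fold cross-validation. Scenarios were 10% against 20% or 25% by arm and, in some runs, 16.7% in both arms. The table gives the share of trials in which at least one noise covariate stays in the tree.

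| Loss | rpart | Separately written trees: minimum error | Separately written trees: one-SE |
|---|---|---|---|
| 1:1 | about 1% minimum error, 0% one-SE | 2-4% | 0% |
| 3:1 | 0-2% | 15% | 2-4% |
| 4:1 | about 5-52% | 38-49% | 11-15% |
| Class-balanced | 53-81% minimum error, 37-68% one-SE | 46-67% | 19-35% |

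A further rpart set exceeded 90% with class-balanced loss, which occurs when the arms quit at the same rate. Without cross-validated pruning, the default rpart tree kept noise in 93-100% of trials.

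The 1:1 and class-balanced rpart rows use 1,000 trials per setting (95% Monte Carlo error at most 1.96×√(0.25/1000) = 3 points). The 3:1 and 4:1 rpart rows use 300 (6 points). The separately written trees used 200 or more (at most 7 points).

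**The case against.** Much of the opposing case stands.

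- A reader might infer from the Significance sentence that even a tree that fails cross-validation goes into medical records. The documents do not say that. *Positive or negative* describes the trial's findings, and the sentence is dissemination language written for the funder. What remains is that practice impact is declared independent of the Aim 1 and 2 results, and that the analysis section sets no condition.
- A reader might infer that a tree without splits is impossible. It is not: pruning can collapse the tree to its root, and the aim itself is worded conditionally. The plan only omits what follows from that result.
- The bootstrap is a real safeguard against overconfident predictions. It describes uncertainty, however, and does not decide use.
- A reader might infer that noise splits are the usual outcome. That holds only for heavy loss or lenient pruning. At 3:1 or below with cross-validated pruning in rpart they almost vanish. The pruning rule may also be settled in the cited source, which cannot be consulted here, so it cannot be assumed either way.

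None of this touches the primary endpoint, the sample size, or Aims 1 and 2.

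**Conclusion.** The point holds in a limited form. I.B promises a property that the design cannot guarantee, and no rule in II.C links the tree's measured performance to its use. The risk of a chance split runs from near 0% to a majority of trials. The upper end rests on class-balanced loss with minimum-error pruning; the one-SE rule lowers it to between about one fifth and two thirds, depending on the implementation. The loss at which the rate starts to climb also differs between implementations, as the 3:1 row shows. The choice that decides the matter is therefore open until outcomes are known.

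The efficacy claim is weaker still. With 12.8 expected quitters in C, a tree of three equal leaves would have about 12.8/3 = 4 C-arm quitters per leaf with which to compare treatment effects.

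Assumptions: about 16 candidates, independent noise covariates, the loss ratios shown, and the plan's expected rates. Part of the protocol between II.H and the safety monitoring text was not available. The change is one that should be made, with moderate confidence in the exact percentages and more in their direction.

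**What to change.** 1. Before outcome data are seen, fix the loss ratio, the pruning rule (for example one-SE) and the performance metric (for example cross-validated deviance or Brier score).
2. Rerun the whole build, prune and cross-validate process on permutations of the covariate rows against the (arm, outcome) pairs; 1,000 would do. Put the tree forward for medical records, as a predictor of quitting, only if its cross-validated gain over the two arm rates exceeds the 95th percentile of the permutations. Show the planned bootstrap intervals with it.
3. Step 2 tests only whether covariates predict quitting, and a purely prognostic tree could pass. Claim subgroups with differing efficacy only if a separate test of treatment-by-leaf interaction also passes, calibrated by resampling under a common treatment effect with the tree rebuilt each time.
4. Otherwise report that no subgroups were found, give the arm rates with confidence intervals, and label the tree exploratory.
5. In I.B, change *will identify* to *will explore whether*.

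The cost is computing time and a short addition to II.C, with no extra participants, visits or assays. The downside is that weak but real subgroups would be published as exploratory only.

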insomnia, and vivid dreams. To address these concerns, participants will receive written information and information from their counselor about how to manage any of these symptoms. They will be given advice on when they might need to reduce their nicotine dose (whether through decreasing smoking or decreasing NRT). We will track adverse events and review adverse events regularly (see data safety and monitoring plan below).

Psychological risk

Risks for participants in both treatment arms (C, C+NRT) also include those associated with the inconvenience of participation including answering surveys, providing urine, and participating in follow-up visits and assessments. To minimize the inconveniences associated with study participation we will review all data collection instruments and study procedures with our Patient Advisory Panel and our Stakeholder Advisory Committee. We will use their input to minimize the number of items in our instruments and improve the accessibility and convenience of our study procedures. We anticipate using several methods to enhance convenience to participants, including offering study visits in the evening and on weekends and offering patients a choice of where they will be seen (KUMC or Swope). Another risk is feeling pressured to be in the study, which we will track in order to monitor and will report this as an adverse event.

Social risk

None

Economic risk

None

Potential benefit of participating in the study

There are also no direct benefits to participating in this study except that researchers hope that the information from this research study may be useful in improving treatment for non-daily smokers.

G. Location where study will be performed:

The study will take place at Swope Health Central, [name], in Kansas, Missouri or at the KUMC CRU in Fairway, Kansas based on the preference of each participant. All data will be directly entered into an electronic data capture system (i.e., RedCap or CRIS), therefore minimizing the use of paper records. If paper records are generated, they will be stored in locked file cabinets at Swope. Only study staff will have access to the locked records at Swope and the secure online electronic data capture system.

H. Collaboration (with another institution, if applicable):

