Consent will be obtained prior to participant involvement. Individuals interested in the proposed study will meet the research assistant at Swope or the CRU. Each individual will be given a copy of the consent form and as much time as they need to review its contents. After the consent form is read, both the individual and the research assistant will review the consent form together and the potential participant will be encouraged to ask questions. Each individual will be reminded that participation in the study is completely voluntary and their decision to participate will not affect their current or future medical care at the treating facility. The consenting process will take place in a private location.

D. Alternatives to Participation

Alternatives to participating in the study are to quit "cold turkey" (without assistance), use other smoking cessation programs, purchase other NRT from their pharmacy, obtain a prescription for varenicline, bupropion or other smoking cessation products from their physician, or continue to smoke.

E. Costs to Subjects

There are no costs to subjects. All tests, procedures, and visits are being performed solely for research purposes and are not billable to insurance companies.

F. How new information will be conveyed to the study subject and how it will be documented

We have plans to publish data from this study in aggregate but will not provide any individualized feedback to participants.

G. Payment, including a prorated plan for payment

Participants will be given a \$40 electronically loaded gift card at Wks 0, 12 and a \$20 electronically loaded gift card at Wks 1, 4, 8, 10, 26 in appreciation for their time and participation. Participants must complete the visit to receive the reimbursement associated with that time point. Travel costs will not be reimbursed. Participants will also be given \$20 for each referral who is eligible and enrolls in the study. Each participant may refer up to 3 total referrals.

H. Payment for a research-related injury

Not applicable

IV. DATA COLLECTION AND PROTECTION

A. Data Management and Security

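### Allocation in this effectively open trial rests on paper envelopes drawn by the research assistant, with no described safeguard against early or out-of-order opening; electronic release from the existing data capture system would close the gap cheaply

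*Combined protocol and SAP*

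**What the plan says.** Section II.C sets the size and split: "384 AA non-daily smokers will be randomized", in a 2:1 ratio favouring C+NRT, and "The maximum number of participants enrolled in C will be 128 and the maximum number enrolled in C+NRT will be 256". The sequence comes from computer-generated random numbers. A member of a named team puts the assignments into sealed envelopes carrying sequential study IDs. Once baseline data are complete, "the research assistant will select the sequential study ID number from the sealed envelope to determine the randomization assignment". The Intervention text in II.E confirms that consent and the baseline survey come before randomisation.

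Section III.C describes consent at either Swope or the CRU, where "both the individual and the research assistant will review the consent form together". Section II.G lets the participant choose the location and says: "All data will be directly entered into an electronic data capture system (i.e., RedCap or CRIS), therefore minimizing the use of paper records". Section IV.E plans no continuing third-party monitoring.

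C receives counselling only and no placebo is described, so the trial is open in effect although the text never uses that word. The primary test is a chi-square comparison of verified abstinence at Week 12, with no covariate adjustment and losses counted as smokers.

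I found no statement of list type, block size, stratification by location, envelope opacity, custody, an opening log, or whether the two locations share one envelope series. A stretch of text between II.H and the adverse-event reporting text was not available to me, so any such detail there is unchecked.

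**The concern.** In an open trial, concealment of the next assignment is the only barrier between knowing an arm and deciding who enters it. Here the barrier is a stack of paper envelopes handled by the role that also takes consent. A sealed envelope hides its content only while it stays sealed and is used in turn. Paper cannot enforce its own order or record when it was opened, and two enrolling locations make order harder to reconstruct.

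Staff who knew the next arm would have room to act on it. II.E allows up to 14 days between initial and final screening, so a visit can be re-timed without refusing anyone, and the criteria on interest in quitting and willingness to use NRT involve judgement. Likely quitters are partly recognisable, for instance by days smoked per month. Selective entry would pass into the primary contrast: intent-to-treat protects the comparison after randomisation, not before it.

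**Working it through.** No arithmetic can show whether envelopes would be opened early. What can be checked is how far the stated ratio and maxima make assignments predictable, and what that could do to the Week 12 test.

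**1. The plan's own figures.** Inputs from II.C: 128 in C, 256 in C+NRT, 10% in C, type 1 error 5%. Power = Φ[(d − 1.96·SE0)/SE1], with SE0 from the pooled rate and SE1 from the separate rates; the opposite tail is negligible.

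| C+NRT rate | d | SE0 | SE1 | Power | Stated |
|---|---|---|---|---|---|
| 25% | 0.150 | 0.0433 | 0.0379 | 95.7% | 95% |
| 22.5% | 0.125 | 0.0419 | 0.0372 | 87.6% | 87% |
| 20% | 0.100 | 0.0403 | 0.0364 | 71.7% | 71% |

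The stated power is reproduced by a two-sided, uncorrected chi-square test. The error rates below use the same test, adding both tails.

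**2. Predictability from the maxima alone.** Once one arm is full, every later assignment is certain.

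- *One shuffled list of exactly 128 and 256.* The expected number of C+NRT places after the last C is 256/129 = 1.98, and of C places after the last C+NRT is 128/257 = 0.50. The total is 2.5 of 384 (0.7%). Simulation gives 2.5, 95th percentile 7.
- *Unrestricted 2:1 numbers stopped at the maxima.* The count in C after 384 draws has SD √(384 × 1/3 × 2/3) = 9.24. An excess of e in C means that C filled about 3e places early; an excess of e in C+NRT means that it filled about 1.5e places early. The mean positive excess on each side is 9.24 × 0.399 = 3.69, so the mean tail is about 3.69 × (3 + 1.5) = 16.6. Simulation gives 16.5 (4.3%), median 13, 95th percentile 44.

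**3. Effect of that tail.** Assume no treatment effect, 10% abstinence, and a 5-point shift from selection at every foreseen place (my assumption).

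- C fills first: mean tail about 22, all C+NRT. Bias 22/256 × 5 = 0.43 points; rejection rate 5.1%.
- C+NRT fills first: mean tail about 11, all C. Bias 11/128 × 5 = 0.43 points; rejection rate 5.1%.
- A tail of 44 (95th percentile): 0.86 points and 5.5% if all C+NRT; 1.7 points and 7.7% if all C.

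**4. Worst case, under a list type that the plan does not state.** With fixed blocks of 3 known to staff, place 3 is always certain, and place 2 is certain when place 1 was C. The share certain is 1/3 + 1/3 × 1/3 = 4/9 = 44% (one third of C, half of C+NRT). Fixed blocks of 6, 9 and 12 give 28.9%, 21.4% and 17.0%. With the same 5-point shift at every foreseen place in blocks of 3, C+NRT becomes 10 + 0.5 × 5 = 12.5% and C becomes 10 − 5/3 = 8.3%. The bias is 4.2 points and the test rejects about 22% of the time. This needs four assumptions together: blocks of 3, staff who know it, a full view of past assignments, and consistent steering.

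**The case against.** A reader might infer that the 2:1 rule and the per-arm maxima together let staff foresee upcoming assignments. The documents do not support that. A ratio and two totals do not reveal a random sequence in sealed envelopes, and 128 and 256 are simply the 2:1 split of 384. The sentence about two C+NRT participants for every C states a ratio, which II.B also gives as percentages; it is not a description of blocks. Nor do the maxima and blocks of 3 reinforce each other: unrestricted numbers have no blocks, and 384/3 = 128 whole blocks would fill both arms only in the last one.

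Other points also stand. A shared job title does not show that one person both consents and allocates. Drawing an assignment after consent and baseline is normal practice and harmful only with foreknowledge. If the locations share a series, an assistant at one may not see what was opened at the other, which weakens prediction. Only people who approach the study are screened, against listed criteria, which limits room to steer. The secondary covariate modelling in II.C includes days smoked per month, so it might reveal an imbalance on that factor, although it does not alter the primary test.

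None of this answers the narrower point. The described safeguards do not stop an envelope from being opened early or out of turn, and no record is described that would show it.

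**Conclusion.** The concern holds as a weakness in the allocation method, not as demonstrated foreseeability or bias. The envelope procedure leaves early or out-of-order opening unprevented and undocumented in an effectively open, two-location trial with an unadjusted primary test. How often that would happen cannot be estimated from the documents.

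The maxima are a negligible part of it: about 2.5 to 16.5 assignments of 384 on average, and roughly 0.4 points of bias at the upper figure under an assumed 5-point steer. The 44% and 22% figures are a worst case resting on assumed fixed blocks of 3 and an assumed steering effect, and should not be cited as properties of this plan. The conclusion also assumes that no custody or logging procedure stands in the text that I could not see. This is a worthwhile improvement because the remedy is cheap, not because an error is proven.

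**What to change.** Amend II.C so that the statistician loads one concealed 2:1 list into the RedCap or CRIS system already used for data entry. The system releases one assignment at a time, time-stamped, for both locations from that single list, and only after eligibility, consent and baseline data are saved. Keep sealed envelopes only as a backup for system downtime, with each use logged.

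State the list type in the restricted randomisation file rather than to site staff. Blocking is not essential: one shuffled list of 128 and 256 meets the planned totals with about 2.5 predictable places. If the list is blocked, use varying block sizes withheld from site staff. Removing the maxima is optional and gains almost nothing.

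The cost is a short amendment, a one-off set-up, and system access at the point of randomisation. With some list types the arm totals may depart slightly from 128 and 256, with negligible effect on power. No extra participants, visits or staff are needed.
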